2.1.4 Detection of Bias

This study has been designed to minimize potential bias by allocating treatment groups randomly, assessing endpoints and handling withdrawals without knowledge of the treatment. Other factors that may bias the results of the study include:

- important protocol deviations likely to impact the analysis and interpretation of the efficacy endpoints
- inadvertent breaking of the blind before formal unblinding
- investigational product dosing non-compliance
- the timing of and reasons for early withdrawal from treatment and from study

The incidence of these factors may be assessed. Important protocol deviations will be listed and/or tabulated in the clinical study report (CSR). If necessary, the incidence of other factors will be tabulated.

2.1.5 Outliers

Histograms will be examined to identify outliers in any of the continuous variables used in the analyses. Unexpected and/or unexplained values in categorical data will be identified by utilizing frequency tables.

Outliers due to data entry errors will be corrected by the study team before final database lock. The validity of any questionable values or outliers will be confirmed. Outliers or any questionable values with confirmed validity will be included in the analyses. However, ad-hoc sensitivity analyses may be conducted to evaluate the influence of extreme values in the data.

2.1.6 Distributional Characteristics

Continuous endpoints of change from baseline value will be analyzed under normality assumption. If they deviate appreciably from normality, appropriate transformations or the non-parametric alternatives will be used, such as Van Elteren statistic ([Van Elteren 1960](#)).

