9.5 Analysis of secondary variables

9.5.1 Efficacy variables

The secondary variables are:

During the Double-Blind Treatment Epoch:

- Change from baseline in monthly migraine days in the last month (month 3) of the double-blind treatment epoch
- Change from baseline to month 3 of the MPFID “impact on everyday activities” domain score
- Change from baseline to month 3 of the MPFID “physical impairment” domain score
- Change from baseline in acute monthly migraine-specific treatment days in the last month (month 3) of the double-blind treatment epoch
- 75% responder rate: Proportion of patients who achieve at least a 75% reduction from baseline in monthly migraine days in the last month (month 3) of the Double-Blind Treatment Epoch.
- 100% responder rate: Proportion of patients who achieve at least a 100% reduction from baseline in monthly migraine days in the last month (month 3) of the Double-Blind Treatment Epoch.

The above continuous endpoints (ie, change from baseline) will be analyzed using a linear mixed effects model including treatment group, baseline value, stratification factor(s), scheduled visit, and the interaction of treatment group with scheduled visit, without any imputation for missing data. The responder endpoints will be analyzed using the same method as for the primary endpoint.

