2.6.2 Statistical methods of analyses

Analysis of secondary efficacy endpoints will utilize the FAS. Subjects will be analyzed according to their randomized treatment group regardless of the actual treatment received during the study.

For efficacy analysis at week 12, the continuous change from baseline efficacy endpoints will be analyzed using a linear mixed effects model including treatment group, baseline value, stratification factor, scheduled visit, and the interaction of treatment group with scheduled visit, without any imputation for missing data.

The dichotomous secondary efficacy endpoints derived from corresponding continuous endpoints will be analyzed using the stratified Cochran-Mantel-Haenszel (CMH) test after the missing data are imputed as non-response.

In all cases, estimates (difference/or odds ratio) of treatment group compared to placebo group with associated 95% confidence intervals and p-values will be provided. Additionally, the estimated common relative risk and risk difference with their asymptotic (Wald) confidence limits will be provided for the dichotomous secondary efficacy variables.

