In Bayesian inference, information about unknown parameters is expressed in the form of a posterior distribution. MCMC has been applied as a method for exploring posterior distributions in Bayesian inference. That is, through MCMC, one can simulate the entire joint distribution of the unknown quantities and obtain simulation-based estimates of posterior parameters that are of interest.

Assuming that the data are from a multivariate normal distribution, data augmentation is applied to Bayesian inference with missing data by repeating a series of imputation and posterior steps. These two steps are iterated long enough for the results to be reliable for a multiply imputed data set ([Schafer 1997](#)). The goal is to have the iterations converge to their stationary distribution and then to simulate an approximately independent draw of the missing values.

Sample SAS code for MI using MCMC method will be provided as instruction to TFLs.

Further, as a sensitivity analysis, the pattern-mixture model approach is used to model the distribution of a response as the mixture of a distribution of the observed responses and a

distribution of the missing responses, for which the missing values can be imputed under a plausible scenario for which the missing data are missing not at random. The control-based pattern imputation, in which, the set of observations from control group are used to derive the imputation model.

Van Elteren Test for Continuous Response Variable with Strata

When assumption of normality in analysis of covariance model is violated, then a Van Elteren's test for stratified continuous data can be used. Van Elteren's test is a nonparametric test that compares treatments in the presence of blocking. The test is an extension of Wilcoxon's rank-sum test ([Van Elteren 1960](#)).

Van Elteren proposed to combine stratum-specific Wilcoxon rank-sum statistics with weights inversely proportional to stratum size.

Suppose that the data obtained for the subjects in two treatment groups are split into J strata. Then, the stratified Wilcoxon test statistic is

$$W^* = \frac{\sum_{j=1}^J a_j (T_j - E(T_j))}{\sqrt{\sum_{j=1}^J a_j^2 \text{Var}(T_j)}}$$

where $j=1, \dots, J$ denote the strata, $(T_j - E(T_j))$ and $\sqrt{\text{Var}(T_j)}$ are the numerator and denominator respectively of the Wilcoxon statistic for the data in strata j and a_j is the weight applied to each strata. The test statistic can be rewritten in the form

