$$W^* = \frac{\sum_{j=1}^J a_j \sqrt{\frac{n_{0j}n_{1j}}{n_{0j} + n_{1j}}} \left(\frac{1}{n_{0j}} \sum_{k=1}^{n_{0j}} R_{0jk} - \frac{1}{n_{1j}} \sum_{k=1}^{n_{1j}} R_{1jk} \right)}{\sqrt{\sum_{j=1}^J a_j^2 \frac{1}{n_{0j} + n_{1j} - 1} \sum_{i=0}^1 \sum_{k=1}^{n_{ij}} (R_{ijk} - \bar{R}_{\bullet j})^2}}$$

where R_{ijk} is the rank of the observation X_{ijk} within strata j , $i=0,1$ denotes the treatment group, $j=1, \dots, J$ denotes the strata, $k=1, \dots, n_{ij}$ denotes the subjects within the i^{th} treatment group in the j^{th} strata and $\bar{R}_{\bullet j}$ is the average rank of all observations in strata j . This form of the test statistic was programmed into the SAS macro used for analyses.

Assuming no ties within the data, the simplified form of the variance, that is

$$\left[\sum_{j=1}^J a_j^2 \frac{1}{12} \cdot n_{0j}n_{1j} (n_{0j} + n_{1j} + 1) \right]$$

can be used.

Two weights have been used to combine results over strata:

$$\text{“Locally best”}: a_j = \sqrt{\frac{n_{0j}n_{1j}}{n_{0j} + n_{1j}}} \cdot \frac{1}{n_{0j} + n_{1j} + 1}$$

$$\text{“Type II” (used for pooled analyses)}: a_j = \sqrt{\frac{n_{0j}n_{1j}}{n_{0j} + n_{1j}}}$$

For large sample sizes (within each strata) the test statistic has a standard normal distribution; therefore the two-sided test would reject the null hypothesis if $|W^*| > u_{\alpha/2}$.

The test can easily be implemented using the SAS, PROC FREQ. The FREQ procedure is used with the TABLE statement options CMH2 and SCORES=MODRIDIT. The second CMH statistic, labeled "Row Mean Scores Differ" is the asymptotic test statistic.

As shown by [Koch et al 1982](#), the Van Elteren test is a member of a general family of Mantel-Haenszel mean score tests. For more information about the Van Elteren test and related testing procedure, refer to [Lehmann 1975](#), [Koch et al 1990](#).

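### SAP 2.1.6 lets an undefined look at normality move the four continuous secondary endpoints off the pre-specified mixed model, and the Van Elteren branch gives no difference with CI

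*SAP*

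**What the plan says.** **Main method.** Protocol 9.5.1: "The above continuous endpoints (ie, change from baseline) will be analyzed using a linear mixed effects model". SAP 2.6.2 repeats this; the Week 12 continuous endpoints "will be analyzed using a linear mixed effects model including treatment group, baseline value, stratification factor, scheduled visit" and the treatment-by-visit interaction, with no imputation. Table 5 lists it as Analysis method IV. Four of the six secondary efficacy endpoints are continuous: change in monthly migraine days, in the two MPFID domain scores, and in acute migraine-specific medication days. The 75% and 100% responder endpoints go to the stratified CMH test.

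**Promised output.** SAP 2.6.2: "In all cases, estimates (difference/or odds ratio) of treatment group compared to placebo group with associated 95% confidence intervals and p-values will be provided".

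**Switch.** SAP 2.1.6 assumes normality for change-from-baseline endpoints and then says: "If they deviate appreciably from normality, appropriate transformations or the non-parametric alternatives will be used". Van Elteren is its example of a non-parametric alternative.

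**Fallback.** SAP 5.4.2: "When assumption of normality in analysis of covariance model is violated, then a Van Elteren's test for stratified continuous data can be used". The appendix shows the statistic in two algebraic forms and says that the second, written in mean ranks, was programmed in the SAS macro. It then offers a shortcut: "Assuming no ties within the data, the simplified form of the variance, that is", followed by a formula. It also gives a PROC FREQ route, whose row-mean-scores statistic "is the asymptotic test statistic".

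**The concern.** The sections cannot all be followed at once. Section 2.1.6 is mandatory once its condition is met, yet the condition is not defined. Section 2.6.2 and Table 5 allow one method only. Appendix 5.4.2 is permissive and refers to ANCOVA, which under SAP 2.6.3 is the sensitivity model (with BOCF), not the main one. Two statisticians could each follow this SAP and report different main analyses of the same endpoint.

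Two things are at stake. One is the estimate: Van Elteren is described only as a test, so a clinician or HTA reader could be left without a difference in migraine days. The other is error control: a choice of method that is open when outcome data are examined can raise the false-positive rate if it is used freely.

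**Working it through.** **1. The plan's own figure.** The documents give no figure for the switch or for the continuous endpoints. The one design calculation (Protocol 9.8, SAP 3) is for the primary responder endpoint: 18% vs 38%, 110 per group, two-sided 0.05. With the usual normal approximation, z = [0.20·√110 − 1.96·√(2·0.28·0.72)] / √(0.18·0.82 + 0.38·0.62) = (2.098 − 1.245)/0.619 = 1.378, so power is 91.6% against the stated 90%. Nothing below alters this.

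**2. What each branch delivers, from the SAP text.**

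| | Mixed model (2.6.2) | Transformation (2.1.6) | Van Elteren (5.4.2) |
|---|---|---|---|
| Difference with 95% CI | yes, in days or points | yes, on another scale | none described |
| Baseline covariate | yes | depends on the model, not stated | no |
| Weeks 4 and 8 | yes | depends on the model, not stated | no |
| Missing Week 12 value | observed data, no imputation | not stated | not stated |

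SAP 2.6.4 also requires subgroup results by the primary method, with adjusted means, SEs, CIs and an interaction p-value. The rank test as described supplies none of these.

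**3. Type I error.** Assumptions, none of them in the documents: 220 patients split 110/110; about 60% in the 8-14 stratum; residual SD of 4 days; normal, gamma-skewed or strongly gamma-skewed errors; no missing data; Week 12 ANCOVA standing in for the mixed model. There were 20,000 null runs per row, so the Monte Carlo SE is √(0.05·0.95/20,000) = 0.15 points.

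| Errors | ANCOVA always | Van Elteren always | Switch if Shapiro-Wilk p < 0.05 | Better of the two | Better of three (log added) |
|---|---|---|---|---|---|
| Normal | 4.95% | 5.04% | 4.99% | 6.2% | 7.7% |
| Skewed | 4.97% | 5.08% | 5.08% | 6.9% | 7.7% |
| Strongly skewed | 5.16% | 5.04% | 5.04% | 7.9% | 8.5% |

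The Shapiro-Wilk trigger fired in about 5% of normal runs and in essentially all skewed ones. With 246 patients (the number randomized), the better-of-two figures were 6.7%, 7.0% and 8.4%.

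**4. The no-ties variance.** Write N_j = n0j + n1j.

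- Rank-sum form (first in 5.4.2): Var(T_j) = n0j·n1j·(N_j+1)/12. This is the printed expression, and it is correct here.
- Mean-rank form (second, said to be programmed): with no ties, the sum of squared rank deviations is N_j(N_j²−1)/12. Dividing by N_j−1 gives N_j(N_j+1)/12, so the variance is Σ a_j²·N_j(N_j+1)/12.

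Putting the printed expression under the mean-rank numerator multiplies the stratum variance by n0j·n1j/N_j, which is N_j/4 under 1:1 allocation. The null SD of the statistic then falls from 1 to 2/√N_j in a single stratum: 0.20 for N_j = 98 and 0.16 for N_j = 148 (an assumed split of the 246). Combined over strata it is 0.18 with the locally best weights and 0.17 with Type II weights. A split of 49/197 keeps it between 2/√197 = 0.14 and 2/√49 = 0.29. At 0.18, reaching 1.96 would take a deviation of about 11 standard deviations.

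**The case against.** Three stronger readings are tempting, and the documents do not support them.

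- *Type I error is inflated.* Section 2.1.6 switches on non-normality, not on the smaller p-value. A mechanical switch held 5.0 to 5.1%. The 6 to 8% figures describe unrestricted choice, which the text does not direct, although it does not exclude it either.
- *A confirmatory method is chosen after treatment effects are seen.* The readable text has no multiplicity procedure for the secondary endpoints, and the one test with a stated significance level is the primary CMH test. Protocol 5.4 keeps the sponsor blinded until the double-blind epoch and primary analysis conclude, and Protocol 8.3 releases codes after lock, so a pooled check without codes is possible. Section 2.1.6 also names no kind of check; the histograms in 2.1.5 are for outliers.
- *The CI is lost for every secondary endpoint.* Two of the six are responder endpoints, and the transformation branch still yields an interval. Because 5.4.2 is permissive and 2.6.2 demands estimates in all cases, one can argue that the mixed model would stay.

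On the formula, the printed variance is right for the first form, applies only without ties, and is bypassed by the PROC FREQ route. A test that never rejects would arise only from combining the two forms.

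What remains is an undefined trigger, an open choice of fallback, a fallback that cannot meet 2.6.2, and sections that disagree on whether it is mandatory.

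**Conclusion.** The point holds as an unresolved inconsistency with a practical consequence, and it should be corrected. If the Van Elteren branch is taken for any of the four continuous secondary endpoints, the plan as written gives a p-value without the promised difference and CI, and discards the baseline covariate and two of the three post-baseline visits. That conclusion rests on the text alone.

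The effect on error rates is conditional: about 5% under a fixed rule, about 6 to 8% if the more favourable of two tests may be taken, and up to 8.5% with a log transformation added. These figures depend on the assumed error shapes, SD and strata. The documents give no distribution for these endpoints, so how likely the trigger is remains unknown; with skewed errors it would almost always fire.

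The variance issue is a labelling mismatch between two forms of one statistic. It matters only if the shortcut is coded with the mean-rank form. The primary analysis and the sample size are untouched.

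**What to change.** - In SAP 2.1.6, state that the mixed model is the main analysis of each continuous secondary endpoint whatever the distribution, and delete the data-driven transformation.
- Report Van Elteren (PROC FREQ, CMH2, modified ridit scores) in all cases as a pre-specified supportive analysis, with a rule for missing Week 12 values. A stratified Hodges-Lehmann shift with CI would give it an estimate.
- Align 2.6.2, Table 5 and 5.4.2 with this. Section 2.10.5 rules out sensitivity analyses for PROs, so it needs an exception for the two MPFID domains.
- In 5.4.2, say that the printed no-ties variance belongs to the rank-sum form, and give Σ a_j²·N_j(N_j+1)/12 for the mean-rank form.

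The cost is SAP wording and one extra table per endpoint. The main test may also have less power than ranks when skewness is marked. Under the assumptions above with a 1.6-day difference (4,000 runs), ANCOVA and Van Elteren had 82.8% and 80.6% power with normal errors, 83.5% and 93.4% with skewed errors, and 83.5% and 99.8% with strongly skewed errors. The rank result would still be shown.

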2.2 Analysis sets

The **Randomized Analysis Set** (RAS) will consist of all participants who received a randomization number, regardless of receiving study medication.

The **Full Analysis Set** (FAS) will consist of all participants who started study medication and have completed at least one post-baseline monthly migraine day measurement in the doubleblind treatment epoch. In FAS, subjects will be analyzed according to randomized treatment, regardless of the actual treatment received. Analyses for efficacy endpoints and patient reported outcomes (PROs) will utilize this analysis set.

The **SAFety analysis set** (SAF) will consist of all randomized subjects who received at least one dose of investigational product and will be analyzed based on actual treatment received. Analyses for safety endpoints and summary of IP administration will utilize this analysis set. Rule of exclusion criteria of analysis sets is presented in [Appendix 5.5](#).

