5.6.2 Discontinuation of study treatment

Discontinuation of study treatment for a patient occurs when study drug is stopped earlier than the protocol planned duration, and can be initiated by either the patient or the investigator.

The investigator must discontinue study treatment for a given patient if, on balance, he/she believes that continuation would negatively impact the risk/benefit of trial participation.

Study treatment must be discontinued under the following circumstances:

- Patient wish
- Pregnancy (see [Section 6.5.6](#) and [Section 7.5](#))
- Use of prohibited treatment as per recommendations in [Table 5-1](#)
- Any situation in which study treatment might result in a safety risk to the patient
- Unsatisfactory therapeutic effect
- Patient's condition no longer requires study treatment
- Any laboratory abnormalities that in the judgment of the investigator, taking into consideration the patient's overall status, prevents the patient from continuing participation in the study

In addition, study treatment should be discontinued under the following circumstances during the PTA- Open-Label Treatment Epoch:

- Upon country-level launch (as specified in [Section 3.1](#))

- Patient is no longer clinically benefitting from treatment in the opinion of the investigator

If discontinuation of study treatment occurs in the Double-Blind Treatment Epoch, the patient should NOT be considered withdrawn from the study, and should continue recording in the eDiary as per protocol. If permanent discontinuation of study treatment occurs during the Open-Label Treatment Epoch or during the PTA-Open-Label Treatment Epoch, the patient should be discontinued from the study.

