Patients who prematurely discontinue the study for any reason should be scheduled for a visit as soon as possible, at which time all of the assessments listed for the final visit (week 12 if during the DBTE, week 168 if during the OLTE, or visit 499 if during the PTA-Open-Label Treatment Epoch) will be performed. At this final visit, the adverse event and concomitant medications should be reconciled on the eCRF. Patients will return for a follow-up visit approximately 16 weeks after their last dose of study medication, and perform the study procedures outlined in [Table 6-1](#) or [Table 6-4](#) or [Table 6-5](#), depending upon the duration of study participation at the time of discontinuation. After study treatment discontinuation from the Double-Blind Treatment Epoch, the patient, if willing, should continue to follow the visit schedule until Week 12 is reached. At a minimum, the following data should to be collected at clinic visits or via telephone visits:

- new/concomitant treatments
- adverse events/Serious Adverse Events

If the patient cannot or is unwilling to attend any visit(s), the site staff should maintain regular telephone contact with the patient, or with a person pre-designated by the patient. This telephone contact should preferably be done according to the study visit schedule.

The investigator must also contact the IRT to register the patient's discontinuation from study treatment. If study drug discontinuation occurs because treatment code has been broken, please refer to [Section 5.5.9](#). Patients who are prematurely withdrawn from the study will not be replaced by an equal number of newly enrolled patients.

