9.1 Analysis sets

The Full analysis set (FAS) will consist of all patients who started study medication and have completed at least one post-baseline monthly migraine day measurement in the double-blind treatment epoch. In FAS, patients will be analyzed according to randomized treatment, regardless of the actual treatment received.

The Safety analysis set (SAF) will consist of all randomized patients who received at least one dose of investigational product and will be analyzed based on actual treatment received.

The open-label analysis set (OLAS) will consist of all patients receiving at least one dose of AMG 334 in the open-label treatment epoch. This analysis set will be used when summarizing data collected during the Open-Label Treatment Epoch.

The PTA analysis set (PTAS) will consist of a subset of OLAS patients receiving at least one dose of AMG 334 in the PTA-Open-Label Treatment Epoch.

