9.4.2 Statistical model, hypothesis, and method of analysis

The primary analyses will compare the 50% response rate, which is defined as the proportion of patients who achieve at least a 50% reduction from baseline in monthly migraine days in the last month (month 3) of the Double-Blind Treatment Epoch, between AMG 334 vs placebo.

A Cochran-Mantel-Haenszel (CMH) test stratified by the migraine frequency (4-7 and 8-14 monthly migraine days strata) will be used under a 2-sided significance level of 0.05 to evaluate the association between the 50% responder rate and the treatment. The p-value of the test, and the estimated odds ratio between AMG 334 and placebo, as well as its 95% confidence interval, will also be reported. Patients with missing monthly migraine day data at month 3 of the double-blind treatment epoch will be imputed as non-responders.

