2.5 Analysis of the primary objective

2.5.1 Primary endpoint

The primary endpoint is the achievement of at least a 50% reduction from baseline in monthly migraine days in the last month (month 3) of the Double-Blind Treatment Epoch.

The primary analysis will contrast active investigational drug versus placebo in the FAS.

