2.5.2 Statistical hypothesis, model, and method of analysis

The following hypothesis refers to alternative hypothesis. For tests of superiority, null hypothesis presuppose no difference between the treatment groups with respect to the parameter of interest.

Primary hypothesis

- The active treatment arm group is superior to placebo with regard to the proportion of patients who achieve at least a 50% reduction from baseline in monthly migraine days in the last month (month 3) of the Double-Blind Treatment Epoch;

$$H_1: \theta_1 > 1$$

where θ_1 is the odds ratio of active over corresponding placebo.

The primary analyses will compare the 50% response rate, which is defined as the proportion of patients who achieve at least a 50% reduction from baseline in monthly migraine days in the last month (month 3) of the Double-Blind Treatment Epoch, between AMG 334 vs placebo. Patients with missing monthly migraine days' data at month 3 of the double-blind treatment epoch will be imputed as non-responders.

A Cochran-Mantel-Haenszel (CMH) test stratified by the migraine frequency (4-7 and 8-14 monthly migraine days strata) will be used under a significance level of 0.025, one-sided (0.05, two-sided) to evaluate the association between the 50% responder rate and the treatment. The estimated common odds ratio, 95% confidence intervals and two-sided p-values will be reported.

Additionally, the estimated common relative risk and risk difference with their asymptotic (Wald) confidence limits will be provided.

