5.1.1 Study drug

Date of first study drug administration (Day 1)

Day 1 is defined as the first day of administration of randomized study drug (AMG334 or matching placebo). All other days will be labeled relative to Day 1. If subject will not be dosed at Day 1, the Study Day 1 is defined as day of randomization.

Date of last study drug administration

The date of last dose of randomized study drug is simply the day of the last dose.

5.1.2 eDiary data

The eDiary includes the following clinical outcome assessments:

- Incidence of headache (ie, migraine with or without aura or non-migraine headache)
- Time of onset of headache
- Time of resolution of headache
- Pain severity per headache
- Symptoms (eg, nausea, vomiting, photophobia, phonophobia)
- Presence of aura
- Use of acute medication during aura or to treat headache

As well as, patient-reported outcomes (PROs) measures of MPFID, [REDACTED]

Missing eDiary data in the calculation of monthly measurements about subjects' migraine and non-migraine headaches will be handled using the following method:

1. For monthly intervals with ≥ 14 days of eDiary days (including retrospective eDiary days) in each interval:

a) Monthly frequency measurements (including migraine days, headache days, [REDACTED] acute medication use, acute migraine specific medication use etc.) will be prorated to 28-day equivalents. Prorated result does not need to be rounded.

b) [REDACTED] impact on everyday activities scores as measured by MPFID will be calculated as the average of observed scores

2. For monthly intervals with < 14 days of eDiary use (including retrospective eDiary days), all monthly measurement will be set as missing and will be handled as described in [Section 5.1.6](#).

Table 8 Rules for handling missing and incomplete eDiary data

Monthly Endpoint	Condition	Proration Method (does not need to be rounded)
Monthly frequency measurements (including migraine days, headache days, [REDACTED] hours of migraine headaches, acute headache medication treatment days, acute migraine-specific medication treatment days)	If diary days in entire baseline or interval post baseline ≥ 14 (including retrospective eDiary days), then do proration; Else monthly measurement is set to missing [diary days is a day with all headache related questions completed retrospectively or not]	Number of observed migraine days * 28/ Number of information days in interval [information day is a diary day or headache day]

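### The full analysis set drops dosed patients who have no post-baseline monthly migraine-day value, so the primary analysis never counts them as non-responders

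*SAP*

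**What the plan says.** **Who is analysed.** Protocol 9.1 defines the FAS as "all patients who started study medication and have completed at least one post-baseline monthly migraine day measurement in the double-blind treatment epoch". SAP 2.2 repeats both conditions, so that patients must have started study drug and "have completed at least one post-baseline monthly migraine day measurement", and assigns all efficacy and patient-reported endpoints to this set. SAP 2.5.1 confirms it for the primary endpoint: "The primary analysis will contrast active investigational drug versus placebo in the FAS".

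**How missing outcomes are treated.** Protocol 9.4.2: "Patients with missing monthly migraine day data at month 3 of the double-blind treatment epoch will be imputed as non-responders". SAP 2.5.2 gives the same rule.

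**When a monthly value is missing.** Under SAP 5.1.2, if a monthly interval has fewer than 14 diary days, counting retrospective entries, "all monthly measurement will be set as missing".

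**What happens after treatment is stopped.** Under protocol 5.6.2, a patient who stops study drug in the double-blind epoch "should NOT be considered withdrawn from the study, and should continue recording in the eDiary as per protocol". In addition, "the patient, if willing, should continue to follow the visit schedule until Week 12 is reached". SAP Table 2 defines the three monthly intervals for such patients.

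**The concern.** The non-responder rule exists so that a patient without a month-3 outcome is not lost from the comparison. The FAS definition removes some of those patients before the rule can act. Whether a dosed patient enters the primary analysis then depends on diary use after randomisation, which treatment or its failure may influence.

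The direction of bias depends on the arm. Losing active-arm patients who would have counted as non-responders raises the active response rate; losing placebo patients raises the placebo rate. The sensitivity analyses do not help, because the logistic model, the generalised linear mixed model, the baseline-carried-forward (BOCF) analysis and the multiple imputations all use the FAS. The randomised set serves only disposition, baseline characteristics and medical history.

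Two other wordings do not fit cleanly:

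- **SAP 5.5, Patient Classification table (Table 10).** The FAS row excludes patients with no post-baseline measurement of the primary efficacy endpoint. This most naturally restates SAP 2.2. Because that endpoint is defined at month 3, however, the row is loose enough to be read as excluding everyone who lacks month 3.
- **SAP 5.1.6.** The BOCF example, for continuous endpoints, describes a patient with every post-baseline value missing. For monthly migraine days such a patient cannot be in the FAS.

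**Working it through.** **1. Who is excluded.** A dosed patient leaves the FAS only if all three monthly values are missing, that is, fewer than 14 diary days in each of months 1, 2 and 3. This takes a month set to missing as not being a completed measurement.

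| Dosed patient | In FAS? | Primary outcome |
|---|---|---|
| Month 3 observed | Yes | As observed |
| Month 1 or 2 observed, month 3 missing | Yes | Non-responder |
| Months 1, 2 and 3 all missing | No | Not counted |

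Only the last row departs from the stated rule for missing month-3 data.

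**2. The plan's own figures.** Protocol 9.8 and SAP 3 assume 18% on placebo, about 20 points more on active, an odds ratio of 2.8, two-sided 0.05, 90% power and 110 per arm.

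- Odds ratio: (0.38/0.62)/(0.18/0.82) = 2.79.
- Power, normal approximation: z = (0.20×√110 − 1.96×√(2×0.28×0.72)) / √(0.38×0.62 + 0.18×0.82) = (2.098 − 1.245)/0.619 = 1.378, which gives 91.6%.
- With a continuity correction, power is 89.0%.

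The stated figures are reproduced, so 38% and 18% are used below.

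**3. How many patients might be affected.** The Amendment 3 rationale in the protocol reports 246 randomised and 242 completing the double-blind epoch, so 246 − 242 = 4 did not complete (1.6%). This is a rough guide and not a bound. Some of the four may never have been dosed, or may have a month-1 value; a completer with a sparse diary could also be excluded. No split by arm is given.

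**4. Effect of counting the excluded patients.** Assume 123 per arm (246 split evenly) and planning rates that hold within the FAS. If k patients in an arm are restored as non-responders, that arm's rate becomes p × (123 − k)/123.

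| k restored | All active: difference, odds ratio | All placebo: difference, odds ratio |
|---|---|---|
| 0 | 20.0 points, 2.79 | 20.0 points, 2.79 |
| 1 | 19.7, 2.76 | 20.1, 2.82 |
| 2 | 19.4, 2.72 | 20.3, 2.85 |
| 4 | 18.8, 2.65 | 20.6, 2.91 |
| 11 | 16.6, 2.41 | 21.6, 3.13 |

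For k = 4, all active: 0.38×119/123 = 0.3676, and (0.3676/0.6324)/(0.18/0.82) = 2.65. All placebo: 0.18×119/123 = 0.1741, odds ratio 2.91. Two in each arm: 0.3738 versus 0.1771, difference 19.7 points, odds ratio 2.77. The row for 11 (11/123 = 8.9% of an arm) only shows the scale; nothing in the documents suggests so large a loss.

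**5. Effect on the test (unstratified).** Near the planned effect, restoring four active patients moves p from 0.0005 to 0.0010. Only a borderline result is fragile. For example, FAS counts of 35/123 versus 22/123 give p = 0.0495, and one more active non-responder (35/124) gives p = 0.054.

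**The case against.** The strongest reply is that this is a deliberate modified intention-to-treat set, stated identically in both documents. SAP 2.5.1 names the FAS before SAP 2.5.2 gives the non-responder rule, so that rule can be read as applying within the FAS, with no breach. Exclusion requires a nearly empty diary for three months, from a patient who needed at least 80% diary compliance to be randomised and who is asked to continue the diary after stopping drug. The usual dropout, with a month-1 value and then a withdrawal, is already counted as a non-responder. SAP 2.3.1 reports the set sizes, and SAP 2.5.3 promises an examination of missing data by arm, with further sensitivity analyses if the loss is substantial or unbalanced. The dosing condition that would remain is also a post-randomisation event. The wording points are secondary: the wider reading of Table 10 would leave the non-responder rule nothing to act on, and the BOCF example concerns a sensitivity method.

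Much of this stands and keeps the point small. It does not remove it. Reading the rule as limited to the FAS explains the exclusion but does not justify it. The extra analyses in SAP 2.5.3 are contingent and name no all-treated set. Dosing given by site staff under blind is much less open to influence by treatment than months of diary entry.

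**Conclusion.** The concern holds. Dosed patients with no post-baseline monthly value are left out of the primary analysis and of every other specified efficacy analysis, although their month-3 outcome is missing and the plan has a rule for that.

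The effect is probably small and its direction is unknown. If all four reported non-completers were dosed and had no monthly value, the odds ratio of 2.79 would become anything from 2.65 to 2.91, and the 20.0-point difference anything from 18.8 to 20.6. This rests on an assumed 123 per arm, the planning response rates and an assumed count. A result near the planned effect would not be overturned. The reason to act is principle and low cost: membership of the primary set should not depend on post-randomisation diary use when the missing outcome can be counted under the existing rule.

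**What to change.** - **Protocol 9.1 and SAP 2.2:** define the FAS as all randomised patients who received at least one dose of double-blind study drug, analysed as randomised, with no post-baseline requirement. Missing month 3 remains non-response in the Cochran-Mantel-Haenszel test.
- **SAP Table 10:** make never having received double-blind drug the only reason for exclusion from the FAS.
- **SAP 2.6.2:** add a sentence that patients without post-baseline data contribute nothing to the observed-data mixed model for the continuous secondary endpoints.

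These patients then enter the BOCF and multiple-imputation sensitivity analyses. SAP 5.1.5 expects every patient in the FAS to have a baseline value, the SAP 5.1.6 example becomes valid, and the stepwise imputation in SAP 5.4.3 already starts from baseline.

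The cost is wording in three places and one added sentence, with no new data or methods. Reported response rates may be slightly lower. If the double-blind analysis is already locked, leave the FAS as it is and report the same test, with non-responder imputation in all randomised and dosed patients, as a supportive analysis, with the number excluded from the FAS by arm.
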